For Cohort 7, a total of 124 mL (31 x 4 mL samples) will be collected from each subject for PK analysis. Approximately 78.5 mL of blood will be collected for the clinical laboratory evaluations and coagulation testing. The total volume of blood collected from each subject in Part 1 Cohort 7 will not exceed approximately 203 mL.

6.7.2 Part 2

A total of 212 mL (53 x 4 mL samples) will be collected from each subject for PK analysis. Approximately 110.6 mL of blood will be collected for the clinical laboratory evaluations and coagulation testing. The total volume of blood collected from each subject in Part 2 is planned not to exceed approximately 322.6 mL, although more may be collected if a decision is made to prolong PK monitoring.

Table 9 Total Volume of Blood to be Collected for Testing: Part 2

Reason for Collection	Number of Samples	Volume per Sample (mL)	Total Volume (mL)
Clinical labs at screening	1	12.5	12.5
Clinical labs during study (check-in, Days 7, 14, 21, 42, 63, 84, 105, and 126 (end-of-study)	9	8.5	76.5
Coagulation	8	2.7	21.6
Pharmacokinetic analysis (predose trough)	13	4.0	52.0
Pharmacokinetic analysis (postdose)	40	4.0	160.0
		Total	322.6

Additional PK samples may be collected at times to be determined based on the results from previous cohorts.

The Principal Investigator, in conjunction with the Sponsor, may collect additional blood if necessary, for repeat laboratory or safety evaluations including AE follow-up.

6.7.3 Part 3

A total of 128 mL (32 x 4ml samples) will be collected for PK Analysis. Approximately 91 mL of blood will be collected for the clinical laboratory evaluations and coagulation testing.

Table 10 Total Volume of Blood to be Collected for Testing: Part 3

Reason for Collection	Number of Samples	Volume per Sample (mL)	Total Volume (mL)
Clinical labs at screening	1	12.5	12.5
Clinical labs during study (check-in, 6 and 48 hours and Days 5, 7, 10, and 14 (end-of-study).	7	8.5	59.5
Coagulation	7	2.7	18.9
Pharmacokinetic analysis	32	4.0	128.0
		Total	218.9

The Principal Investigator, in conjunction with the Sponsor, may collect additional blood if necessary, for repeat laboratory or safety evaluations including AE follow-up.

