6.9.5 Electrocardiograms

For Part 1, triplicate ECGs will be completed at screening, Day -1, 48 hours, and Day 8 or early withdrawal only. All other time points will be single ECG readings within 15 minutes of time points on Table 15.

The predose ECG will be performed prior to the predose blood draw. If a subject experiences a postdose QTcF >500 msec or a change from baseline QTcF >60 msec, after repeat testing, additional ECGs should be recorded until normalization or return to baseline.

For Cohort 7, all ECGs will be triplicate at each time point. In addition, subjects in will have triplicate ECGs at 16 hours postdose.

For Part 2, triplicate ECGs will be completed at screening, Day -1, Day 15 or early withdrawal only. All other time points on Table 16 will be single ECG readings. ECGs

may be done within 2 hours prior to time of dosing and at 6 hours after dosing on Days 1, 2, 3, 8, 12, 14, and on Days 42, 63, 84, 105, and 126.

For Cohorts 2 and 3, an additional ECG extraction will occur at 16 hours postdose on Day 1 and Day 14. For Cohort 3, all ECGs performed will be triplicate ECGs at each time point listed in Table 16.

For Part 3, triplicate ECGs will be completed with 15 minutes at all timepoints on Table 17.

NOTE: Where possible, ECG extractions should be taken from the continuous 12-lead ECGs (Holter).

The predose ECG should be completed within 1 hour prior to the predose blood draw. If a subject experiences a postdose QTcF >500 ms with a change from baseline QTcF >60 ms, after repeat testing, the Principal Investigator should be notified, and additional ECGs should be recorded until normalization or return to baseline.

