- l. Postdose blood plasma samples will be drawn at the following timepoints:
 - Day 1: 0.5, 1, 2, 3, 4, 5, 6, 8, 10, 12, 16, 20, 24 (pre-dose sample for Day 2).
 - Day 14: 0.5, 1, 2, 3, 4, 5, 8, 12, 16, 20, 24, 28 32, 36, 40, 44, 48, 54, 60, 66, 72, 80, 88, 96, 120, 144, and 168 hours after dosing and on Days 42, 63, 84, 105, and 126.

Additional or fewer samples may be collected at times to be determined based on the results from previous cohorts.

- m. Continuous 12 lead Holter recording (cardiac telemetry) will begin at least 1 hour before and end at least 24 hours after dosing (Day 1) and start again at least 1 hour before and end at least 24 hours after dosing on Day 14.
- n. ECGs extractions from the 12 lead Holter monitor will occur only on Days 1 and 14 at the following time points: 0, 0.5, 1, 1.5, 2, 3, 4, 5, 6, 7, 8, 12, 20, and 24 hours postdose. If a subject experiences a post-dosing QTcF >500 msec or a change-from-baseline QTcF >60 msec, after repeat testing, additional ECGs should be recorded until normalization or return to baseline. For Cohorts 2 and 3, an additional extraction will be done at the 16 hour time point on Days 1 and 14.

NOTE: when ECG extractions coincide with safety ECGs, vital sign assessments, and/or blood draws, then procedures should be carried out in said order.

Global Alliance for TB Drug Development

CONFIDENTIAL

Table 17 Schedule of Assessments and Procedures, Part 3 BA

PART 3	SCR																CON	FINI	ЕМЕ	NT														*FU
STUDY DAY	-21 to -2	-1 CI			DAY 1 0.5 1 1.5 2 3 4 5 6 7 8									TUD					AY 2						3			4		5, 6, 7, 8	10, 14, 21			
EVENT			0	0.5	1	1.5	2	3	4	5	6	7	8	10	12	16 ^a	20	24	28	30	32	36	40	42	44	48	54	60	66	72	80	88		N/A
Informed consent and medical history	X																																	
Height	X																																	
Weight	X	X																																
Physical examination	X	X																X								X							X	
Heart murmur ^b	X	X	X									X						X								X							X	
Vital signs (blood pressure, pulse, temperature, respiration rate, and pulse oximetry)	Xc	X	X°	X	X	X		X	X		X		Х		X		X	X		X		X				X				X			X	X
12-lead safety ECGs	X ^d	X	X ^d	X	X	X	X	X	X	X	X	X	X		X	X	X	X								X							X ^d	X ^d
HIV/hepatitis B, C	X																																	

Protocol TBAJ-876-CL-001 version 8.0

PART 3	SCR																CON	FINE	EME	NT														*FU
STUDY DAY	-21 to -2	-1 CI]	DAY	1										DA	AY 2						3			4		5, 6, 7, 8	10, 14, 21

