## 6.2.11 Concentration-Time Data

Blood Samples for PK analysis in plasma will be collected at:

Part 1 (SAD):

- Predose, and 0.5, 1, 2, 3, 4, 5, 6, 8, 10, 12, 16, 20, 24, 28, 32, 36, 40, 44, 48, 54, 60, 66, 72, 80, 88, 96, 120, 144, and 168 hours after dosing, then on Days 10, 14, 17, 21 and 28.

Additional samples will be drawn on Days 42, 56, and 70 for Cohorts 4, 5, and 6.

- For Cohort 7, PK samples will be collected at predose (0), and 0.5, 1, 2, 3, 4, 5, 6, 8, 10, 12, 16, 20, 24, 28, 32, 36, 40, 44, 48, 54, 60, 66, 72, 80, 88, 96, 120, 144, and 168 hours (Day 14) after dosing.

Part 1 (FE):

- Predose, and 0.5, 1, 2, 3, 4, 5, 6, 8, 10, 12, 16, 20, 24, 28, 32, 36, 40, 44, 48, 54, 60, 66, 72, 80, 88, 96, 120, 144, and 168 hours after dosing, then on Days 10, 14, 17, 21 and 28.

Part 2 (MAD):

- Day 1: Predose, and 0.5, 1, 2, 3, 4, 5, 6, 8, 10, 12, 16, 20, 24 (pre-dose sample for Day 2).

QMD Ref: Worldwide-TMP-ST-006-4.0 Effective: 12Aug2019	Governing QMD: Worldwide-SOP-ST-001
Confidentiality Statement	

This document is the property of Worldwide Clinical Trials Inc. and may not be duplicated, copied, altered or removed from company without prior approval from Worldwide Quality Assurance or in compliance with Worldwide Standard Operating Procedures.

Worldwide Clinical Trials Controlled Quality Management Document		
 WORLDWIDE CLINICAL TRIALS	Sponsor:	Global Alliance for TB Drug Development
	Protocol Number:	TBAJ-876-CL001
STATISTICAL ANALYSIS PLAN – PHASE 1		

- Day 14: 0.5, 1, 2, 3, 4, 5, 8, 12, 16, 20, 24, 28, 32, 36, 40, 44, 48, 54, 60, 66, 72, 80, 88, 96, 120, 144, and 168 hours after dosing and on Days 42, 63, 84, 105, and 126.
- Additional or fewer samples may be collected at times to be determined based on the results from previous cohorts. Predose trough concentrations will be collected daily from Days 2 through 13.

Part 3 (RBA and FE):

- Pre-dose, and 0.5, 1, 2, 3, 4, 5, 6, 8, 10, 12, 16, 20, 24, 28, 32, 36, 40, 44, 48, 54, 60, 66, 72, 80, 88, 96, 120, 144, and 168 hours after dosing, then on Days 10 (240 h) and 14 (336 h).

Concentration-time data will be tabulated by part, nominal time, analyte, cohort (group for Part 3), and study day (for Part 2) using descriptive statistics. For presentation of the individual data and summary statistics, concentrations below the limit of quantitation (BLQ) will be set to zero.

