### 6.2.12.2.2 Study Day 14 PK Parameters (Part 2)

The following PK parameters will be calculated for TBAJ-876, M2, and M3 for Part 2 (Day 14):

Parameter	Definition
$C_{\max}$	Maximum plasma concentration, determined directly from individual concentration-time data
$T_{\max}$	Time of the maximum plasma concentrations
$C_{\min}$	Minimum plasma concentration, determined directly from individual concentration-time data
$AUC_{\text{tau}}$	Area under the plasma concentration-time curve over the 24 hour dosing interval, calculated using the linear trapezoidal rule
$C_{\text{avg}}$	Average plasma concentration over 24 hours
$C_{24}$	Plasma concentration at 24 hours postdose
$C_{\text{trough}}$	Predose plasma concentration, (Days 2-14)
$\lambda_z$ ( $K_{\text{el}}$ , Lambda z)	The apparent elimination rate constant $\lambda_z$ will be calculated as the negative of the slope of the linear regression through the terminal log-linear segment of the plasma concentration-time curve; the range of data to be used will be determined by visual inspection of a semi-logarithmic plot of concentration vs. time  (see additional criteria in Section 6.2.12.3)  (may be calculated as reasonable)
$t_{1/2}$	The observed terminal elimination half-life, calculated as: $t_{1/2} = \ln(2)/\lambda_z$ (may be calculated as reasonable)
$CL_{\text{ss}}/F$	The apparent total plasma clearance after an oral dose at steady-state, calculated as:

QMD Ref: Worldwide-TMP-ST-006-4.0 Effective: 12Aug2019	Governing QMD: Worldwide-SOP-ST-001
Confidentiality Statement	

This document is the property of Worldwide Clinical Trials Inc. and may not be duplicated, copied, altered or removed from company without prior approval from Worldwide Quality Assurance or in compliance with Worldwide Standard Operating Procedures.

Worldwide Clinical Trials Controlled Quality Management Document					
 WORLDWIDE CLINICAL TRIALS	Sponsor:	Global Alliance for TB Drug Development			
Protocol Number: TBAJ-876-CL001					
STATISTICAL ANALYSIS PLAN – PHASE 1					

Parameter	Definition
	CLss/F=Dose/AUC tau , where F is the bioavailability (calculated for parent only)
Vz/F	The apparent volume of distribution after an oral dose at steady-state, calculated as: Vz/F=Dose/(AUC inf x λ z ), where F is the bioavailability (calculated for parent only)
R AUC	Accumulation ratio of AUC tau for Day 14, calculated as: AUC tau (Day 14)/AUC tau (Day 1)

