R C24	Accumulation ratio of R C24 for Day 14, calculated as: C 24 (Day 14)/ C 24 (Day 1)
R Cmax	Accumulation ratio of C max for Day 14, calculated as: C max (Day 14)/ C max (Day 1)

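### Part 2 samples Day 1 at 6 h and 10 h but not Day 14, so the Cmax accumulation ratio compares maxima from unequal grids and can only err low relative to matched sampling

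*Protocol*

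**What the plan says.** Table 16, footnote l (Protocol Section 13) lists the Day 1 postdose samples as "Day 1: 0.5, 1, 2, 3, 4, 5, 6, 8, 10, 12, 16, 20, 24 (pre-dose sample for Day 2". The Day 14 list starts "Day 14: 0.5, 1, 2, 3, 4, 5, 8, 12, 16, 20, 24" and then runs on to 168 h. SAP 6.2.11 gives the same Day 14 times: "Day 14: 0.5, 1, 2, 3, 4, 5, 8, 12, 16, 20, 24, 28, 32, 36, 40, 44, 48, 54".

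SAP 6.2.12.2.2 defines Day 14 Cmax as "Maximum plasma concentration, determined directly from individual concentration-time data", with no interpolation, and RCmax as Day 14 Cmax divided by Day 1 Cmax. The same section also defines RAUC and RC24.

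On volume, Protocol 6.7.2 states: "A total of 212 mL (53 x 4 mL samples) will be collected from each subject for PK analysis". Footnote l leaves some room: "Additional or fewer samples may be collected at times to be determined based on the results from previous cohorts". Neither document explains why the two times are missing on Day 14, and neither plans a matched-time analysis.

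**The concern.** Day 14 jumps from 5 h to 8 h and from 8 h to 12 h. A peak inside either gap is missed on Day 14 but could be caught on Day 1. Because RCmax sets one day against the other, the unequal grids do not cancel, and the error has only one direction. At stake are RCmax, which SAP 3.1 names among the Day 14 parameters, and the descriptive Day 14 Cmax and Tmax. A reader could take part of a sampling artefact for less accumulation of the peak than there was.

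**Working it through.** **1. Compare the lists.** Over 0-24 h postdose, Day 1 has 13 times and Day 14 has 11. The difference is exactly {6 h, 10 h}. Day 14 through 168 h has 27 times.

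**2. Reproduce the plan's own count (Table 9).** Postdose: 13 + 27 = 40, as stated. Predose: 14 daily troughs, less the Day 2 trough that doubles as the Day 1 24 h sample, = 13, as stated. Then 13 + 40 = 53 and 53 x 4 mL = 212 mL. Adding 12.5 + 76.5 + 21.6 = 110.6 mL gives 322.6 mL, as stated. With 6 h and 10 h on Day 14 the postdose count would be 42, so the omission is built into the plan and is not a fault of the printed list. (The 40 also leaves out the draws on Days 42 to 126; that is a separate matter.)

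**3. Direction.** Let S1 be the Day 1 times and S14 the Day 14 times up to 24 h, with S14 contained in S1. Planned RCmax = max over S14 of the Day 14 curve / max over S1 of the Day 1 curve. Thinning the numerator cannot raise it, so planned RCmax is at or below the ratio on S1 for both days. Thinning the denominator cannot raise that either, so planned RCmax is also at or below the ratio on S14 for both days. No assumption is needed.

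**4. Size.** No human Tmax is given, so it was varied. The documents' one steady-state prediction (Protocol Table 1 footnote: 25 mg daily, Day 28, Cmax 0.11 µg/mL, AUC0-24h 2.1 µg·h/mL) implies Cmax/Cavg = 0.11 / (2.1/24) = 1.26, a flat profile. The simulation used 14 daily doses, first-order absorption with a lag of 0 to 5 h, two-phase disposition, and a terminal half-life of 168 h (the planning value of about 7 days in Protocol Section 3). About 8,000 parameter sets were drawn over assumed ranges. The shift below is Day 14 Cmax on the planned times against the Day 1 times, without noise. RCmax shifts by the same percentage.

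| True Day 14 Tmax | Profiles | Median shift | Worst shift |
|---|---|---|---|
| up to 5.3 h | all | 0% | 0% |
| 5.5-6.5 h | all | -1% | -21% |
| 5.5-6.5 h | Cmax/Cavg 1.15-1.4 | -1.6% | -7% |
| 5.5-6.5 h | Cmax/Cavg above 1.6 | -8% | -21% |
| 6.5-7.5 h | all | 0% | -7% |
| 7.5-9 h | all | 0% | -0.2% |
| 9-11 h | all | -0.5% | -3.5% |

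AUCtau changed by about 0.2% as a rule and 4% at most.

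**5. Noise.** A maximum over fewer noisy points is lower on average even when the peak is not missed. With an assumed residual CV of 10% and 15%, the mean shift was -2.7% and -3.5% for a profile peaking at 6.2 h, and -3.8% and -5.0% for one peaking at 5.3 h.

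**6. What a common grid does.** In a sharp example (absorption 1.2/h, lag 4.5 h, fast half-life 1.5 h carrying 96% of the weight; Day 14 peak at 5.8 h), RCmax is 1.50 with all Day 1 times on both days, 1.22 as planned, and 1.70 with 6 h and 10 h dropped from both days. In the broader profile peaking at 6.2 h the three are 2.78, 2.75 and 2.79. The common grid removes the mismatch, but it can overshoot when the peak is sharp, because the Day 1 peak stands higher above its background and loses more.

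**7. Mixed grids across cohorts.** Take doses of 25, 75 and 200 mg (200 mg appears in the SAP Section 9 titles; the protocol synopsis has the third dose to be determined). Log-dose deviations are -1.059, 0.039 and 1.020, with sum of squares 2.164. If only the third cohort regained the two samples while the others stayed 14% low, the power-model slope would rise by 1.020 x (-ln 0.86) / 2.164 = 1.020 x 0.151 / 2.164 = 0.07. With a 7% loss the rise is 1.020 x 0.073 / 2.164 = 0.03.

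**The case against.** The strongest reply is that the premise of a peak near 6 h is not in the documents. ECGs are set "at 6 hours after dosing on Days 1, 2, 3, 8, 12, 14" (Protocol 6.9.5), but 6 h is one of 14 Holter extraction times on Days 1 and 14, and the profile-day vital signs are at 0, 1, 6 and 12 h. That pattern does not show that a peak is expected at 6 h. The predicted profile is flat, accumulation is also reported as RC24 (which uses neither time) and RAUC (which hardly does), and footnote l allows samples to be added. All of this limits the size. It does not remove the mismatch, since the clause schedules neither time and no matched analysis is planned.

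A reader might also infer four wider consequences that the documents do not support.

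- **Escalation.** Protocol Section 3 includes the Day 14 profile in the review, but Section 1.7 bases the described dose choices on predicted 24-hour AUC and total exposure, not Cmax.
- **Dose-proportionality slope.** All cohorts share the Day 14 grid, so a common proportional loss goes into the intercept.
- **Concentration-QTc.** The SAP specifies no such analysis; 6.11.6 is descriptive and 6.11.7 lists Holter start and stop data. The Day 14 6 h ECG does lack a paired concentration, but so do the 1.5 h and 7 h extractions on Day 1.
- **Day 14 as the highest exposure in the trial.** Scaling the protocol's predictions linearly and ignoring food, Cmax after a single 800 mg dose is 2 x 0.688 = 1.38 µg/mL, against 8 x 0.11 = 0.88 µg/mL for 200 mg daily.

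**Conclusion.** The point holds for RCmax and for the descriptive Day 14 Cmax and Tmax. The direction is certain: against matched sampling, the planned ratio is equal or low. The size depends on an unstated Tmax. With a peak at 5.5 to 6.5 h and the flat profile the documents predict, the noise-free shift is about 1% to 7%; it reaches about 20% only for a sharp peak in that window. Without noise it is about zero for a peak at or before 5.3 h or at 7.5 to 9 h; assay and within-subject noise could add a few percent. The missing 10 h sample matters little. These figures rest on the assumed model and ranges, not on trial data. This is a minor point with a cheap remedy.

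**What to change.** In SAP 6.2.12.2.2, add RCmax for all cohorts on the common 0-24 h times, taking Day 1 Cmax without the 6 h and 10 h samples, and report it beside the ratio from all samples. Step 6 shows why both are needed: neither alone need equal the ratio from full sampling on both days. State that Day 14 Tmax cannot fall between 5 h and 8 h. This needs no new data and costs one extra summary line per analyte and cohort.

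If any cohort is still undosed, add 6 h and 10 h to its Day 14 list in Table 16 and SAP 6.2.11. Subjects are confined to Day 21, so the cost is two 4 mL draws. On Table 9's own count the PK volume becomes 55 x 4 = 220 mL and the total goes from 322.6 to 330.6 mL, so Table 9 and Protocol 6.7.2 need updating. In that case keep every cross-cohort comparison of Day 14 Cmax, including dose proportionality, on the common grid, so that the sampling change is not confounded with dose (step 7).

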APPENDIX 1 PHARMACOKINETIC SAMPLE COLLECTION, PROCESSING, AND SHIPMENT INSTRUCTIONS

Collection and Processing

A more detailed description of plasma sample preparation requirements may be provided by the analytical laboratory. If such a description is provided, the method of sample preparation provided by the laboratory shall supersede those provided in this protocol and appropriate documentation shall be placed in the Investigator Site File (ISF).

	Processing Instructions
1	Samples will be collected via direct venipuncture at the time points delineated in the appropriate Events Schedule (Section 13).
2	Blood will be drawn into pre-chilled 4 mL evacuated tubes containing K ₃ -EDTA and immediately placed on wet ice and then processed to plasma within 60 minutes.
3	Samples will be centrifuged at 1500 g at approximately 4°C (± 10 degrees) for 10 minutes. After centrifugation, two aliquots of plasma (the first containing at least 0.5 mL and the second containing the remainder of the plasma) will be removed and placed in appropriately labeled 1 mL polypropylene vials.
4	The aliquots will be immediately placed on dry ice. Within 90 minutes of collection, the aliquots will be stored in a freezer set at -80°C \pm 10°C and remain in the freezer until transferred for analysis.
5	Samples will be transferred at the agreed upon intervals.
6	The aliquots will be transferred on dry ice to the Alliance Pharma, Inc. bioanalytical laboratory for the determination of plasma concentrations of TBAJ-876 and its metabolites (M2 and M3) using a validated procedure at Alliance Pharma.
7	Blood sampling, plasma processing, and storage time will be documented in the study records.

Labeling of aliquot tubes

Labels will contain at least the following information:

- a) Study number
- b) Subject identification
- c) Period or dosing phase; sampling time (relative to dosing)
- d) Aliquot letter (a or b)

Shipment

- 1. The samples will be transferred to the analytical laboratory after completion of the study or at mutually agreed upon time points during the clinical conduct of the study. The second set of samples will be shipped after the bioanalytical laboratory confirms receipt of the first set of samples.
- 2. Samples will be packaged into cryoboxes and sorted by subject
- 3. Before shipment, the samples will be appropriately packed in a cooler containing dry ice. Sufficient dry ice will be added to ensure that the samples will remain frozen for at least 72 hours.

APPENDIX 2 DESCRIPTION AND COMPOSITION OF TEST PRODUCT

Description of the Dosage Form

TBAJ-876 Oral Suspension is a compounded preparation at 5 mg/mL TBAJ-876 as tartrate, in ORA-Sweet[®]. The suspension is compounded at the clinical study site with TBAJ-876 tartrate and ORA-Sweet[®], a commercially available flavored suspending vehicle.

Placebo for TBAJ-876 Oral Suspension is ORA-Sweet[®], the same flavored vehicle used in the active oral suspension (without TBAJ-876). The placebo suspension, 100% ORA-Sweet[®], is purchased commercially by the clinical site.

The required doses of the suspension drug product are dispensed using commercially available oral syringes of suitable capacity.

TBAJ-876 Tablets 25 mg are white to off white, round uncoated tablets, plain on both sides.

TBAJ-876 Tablets 100 mg are white to off white, capsule-shaped uncoated tablets, plain on both sides.

Composition of the Drug Product

TBAJ-876 Oral Suspension

The quantitative composition, function, and quality of each ingredient in the drug product (TBAJ-876 Oral Suspension, 5 mg/mL) is provided in the table below.

Qualitative and Quantitative Composition of the TBAJ-876 Oral Suspension, 5 mg/mL

Ingredient	Function	Quality Standard	Quantity in 5	Quantity	per Dose			.,g	
			mg/mL	10 mg	25 mg	50 mg	100 mg	200 mg	400 mg
TBAJ-876 Tartrate ¹ , equivalent to TBAJ-876	Drug Substance	In-house	0.5 g	10 mg	25 mg	50 mg	100 mg	200 mg	400 mg
ORA- Sweet ^{®2}	Flavored Oral Suspending Vehicle	Commercially available	q.s to 100 mL	q.s. to 2 mL	q.s. to 5 mL	q.s. to 10 mL	q.s. to 20 mL	q.s. to 40 mL	q.s. to 80 mL
Total Volum	ne		100 mL	2 mL	5 mL	10 mL	20 mL	40 mL	80 mL

¹TBAJ-876 equivalent calculated using the assay value of free base from the certificate of analysis.

$$\textit{Quantity of Tartrate salt } (g) = \frac{5 \, \frac{\text{mg}}{\text{mL}} * 100 \, \text{mL(volume of suspension)}}{\frac{\% \, \text{assay value as free base}}{100} * 1000 \, \frac{\text{mg}}{\text{g}}}$$

²Purified water, sucrose, glycerin, sorbitol, and flavoring. Buffered with citric acid and sodium phosphate. Preserved with methylparaben and potassium sorbate.

TBAJ-876 Tablets

Each 25 mg tablet contains 25 mg of TBAJ-876 equivalent to 30.7 mg of TBAJ-876 tartrate. Each 100 mg tablet contains 100 mg of TBAJ-876 equivalent to 122.8 mg of TBAJ-876 tartrate. The composition of the tablets is as follows: lactose monohydrate, microcrystalline cellulose, povidone, crospovidone, colloidal silicon dioxide, and magnesium stearate. The formulation of the two strengths of tablets is identical and dose proportional.

Container and Closure System

TBAJ-876 tartrate drug substance is shipped to the clinical study site in double LDPE bags, with each bag individually twist-tied. The bags are then placed in an aluminum foil polybag with a silica gel pack in the foil bag, and heat-sealed.

TBAJ-876 Oral Suspension is transferred and stored in Pyrex glass reagent bottles with a polypropylene (PP) screw cap without a liner. These bottles are used for mixing, sampling, and storage prior to administration.

TBAJ-876 Tablets 25 mg are packaged as 30-count in 30 cc round high-density polyethylene (HDPE) bottles induction sealed and with 28 mm polypropylene (PP) child resistant closures (CRC). TBAJ-876 Tablets 100 mg are packaged as 30-count in 40 cc round HDPE bottles induction sealed and with 33 mm PP CRC. The tables are stored at 15-30 °C (59-86 °F).

